## 7. RATIONALE AND BACKGROUND

RA is a chronic and systemic inflammatory disease with an estimated prevalence of 0.5-1.0% and a mean annual incidence of 0.02-0.05% within Northern European and North American populations. RA is characterised by inflammation, joint destruction, and progressive disability. Joint destruction is frequently irreversible resulting in significant cumulative morbidity. Patients experience a broad range of co-morbidities. Compared with the general population, RA patients are at a higher risk of infections, CV disease (CVD) and malignancies (including lymphoma). These patients are also treated with multiple classes of agents, including nonsteroidal anti-inflammatory drugs (NSAIDs), glucocorticoids, and DMARDs including biologicals, each of which carry significant risks as well as benefits.

Rituximab is a genetically engineered chimeric mouse/human monoclonal IgG1k antibody targeting the transmembrane CD20 antigen. CD20 is a 32-kDa, non-glycosylated transmembrane phosphoprotein, located on the surface of normal precursor-B cells, mature B lymphocytes and malignant B cells. The natural ligand for CD20 has not been identified, and the biological function of CD20 remains unclear. Rituximab binds to a discontinuous conformational epitope on CD20 and initiates multiple immune effector functions leading to target cell lysis. The currently approved indications for licensed rituximab (MabThera) are for Rheumatoid arthritis (RA), Non-Hodgkin's lymphoma (NHL), Chronic lymphocytic leukaemia (CLL), Granulomatosis with polyangiitis (GPA), Microscopic polyangiitis (MPA) and Pemphigus Vulgaris (PV).

Licensed as MabThera in the European Union (EU) in 1998, rituximab was the first biologic on the market for RA for specific B cell targeting therapy. Rituximab in combination with methotrexate is indicated for the treatment of adult patients with severe active RA who have had an inadequate response or intolerance to other disease-modifying antirheumatic drugs (DMARDs) including one or more tumour necrosis factor (TNF) inhibitor therapies.

Biosimilars and non-originator biologicals of rituximab have been approved in several additional countries as of July 2018, including Turkey, Russia, Argentina, South Korea, Australia, and India. The European Medicines Agency (EMA) approved 2 rituximab biosimilars from 2 MAHs including Rixathon (Sandoz) in June 2017, and Truxima (Celltrion) in November 2018. PF-05280586 (Ruxience) has been developed by Pfizer as a biosimilar to the licensed reference product MabThera and was approved in the EU on 01 April 2020.

The Market Authorisation Holder (MAH) proposes the assessment of safety events of special interest based on the Ruxience EU RMP version 1.0 (infections including serious infections (Important Identified Risk), malignancies (Important Potential Risk), impact on cardiovascular disease (CVD) (Important Potential Risk) and use in pregnancy (Missing Information)).

This non-interventional study is designated as a Post-Authorization Safety Study (PASS) and is conducted voluntarily by Pfizer. This study is designated as a “Category 4 Additional Pharmacovigilance Activities” in line with the reference product.

## 8. RESEARCH QUESTION AND OBJECTIVES

The main research question is to estimate incidence rates of safety events of special interest in patients with RA who are enrolled in ARTIS and initiate treatment with Ruxience.

### Objectives:

To estimate incidence rates of infections, including serious infections, malignancies, cardiovascular events, and use during pregnancy among RA patients in the ARTIS register who initiate treatment with Ruxience.

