### 9.3. Variables

This study will use data routinely captured in the ARTIS register, which include baseline patient characteristics (ie, demographic and clinical characteristics, comorbidities and current and past therapies, and safety events of special interest including serious infections, all malignancies, CVD events, and use during pregnancy. Infectious and cardiovascular events will be ascertained through record linkage with the Swedish Patient Register, which collects information on all hospitalised patients, and all visits to non-primary outpatient care. Diagnoses are assigned by the discharging/treating physician, as well as date of discharge/visit, hospital and department. Malignancies will be ascertained through linkage with the Swedish Cancer Register which contains data on date of cancer diagnosis and type of cancer according to the International Classification of Disease (ICD). classification. Use in pregnancy will be assessed through additional linkage with the Medical Birth Register which contains data from antenatal, obstetric, and neonatal records, and covers all live and still births (but not all miscarriages) in Sweden.

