### 9.3.3. Endpoints of Interest

For the interim and final safety reports (which will include information on patients, covariates and incidence rates for pre-specified safety outcomes, from SRQ as well as from the linked Patient/Prescribed Drug and other registers), the following events of interest have been pre-specified.

1. Hospitalised infections overall.
2. NMSC.
3. Malignancies, excluding NMSC.
4. CV events, including but not limited to deep vein thrombosis/pulmonary embolism.
5. Use during pregnancy.

In addition, the final study report will include the number of Ruxience-exposed pregnancies. If data are sufficient, rates of diagnosed malformations can be provided however, the number of Ruxience-exposed pregnancies is expected to be low based on previous data for other biosimilars.

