#### **9.4.3. The Patient Register and the Prescribed Drug Register**

The Swedish Patient Register provides information on all hospitalised (inpatient treated) patients, and all visits to non-primary outpatient care (such as a visit to a rheumatologist). Diagnoses are assigned by the discharging/treating physician, as well as date of discharge/visit, hospital and department. Diagnoses are coded according to the International Classification of Diseases (ICD), with version 8 used until 1986, version 9 1987 to 1996 and ICD10 since 1997.

The Prescribed Drug Register provides all retrievals of prescribed drugs in Sweden from July 2005 and may be used to aid correct classification of patients by their history of retrieved DMARDs.

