**Table 2. Precision Estimates Based on Incidence Proportions for Safety Events Reported in the Ruxience RMP**

Condition	Incident Count	Population at Risk	Incidence Proportion	Lower Bound of 95% CI	Upper Bound of 95% CI
Any infection (including serious infection)	22	73	0.301	0.199	0.420
Serious infection	3	73	0.041	0.009	0.115
Malignancy (excluding NMSC)	1	73	0.014	0.000	0.074
NMSC	0	73	0.000	0.000	0.049
CV events	3	73	0.041	0.009	0.115

NMSC, non-melanoma skin cancer; CV, cardiovascular; CI, confidence interval.

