**ANNEX 1. LIST OF STAND ALONE DOCUMENTS**

**Table 3. Endpoint Algorithms and Validation References**

Event	Operationalisation	Validation ICD
Serious infections	Hospitalisations in the Patient Register listing as main diagnosis ICD10-codes below. If main diagnosis is RA, contributory diagnoses are also considered. A00-B99 (excluding A33 and A50), D73.3, E32.1, G00-G02, G04.2, G05-G07, H00.0, H44.0, H60.0-H60.3, H66-H67, H70, I30.1, I40.0, J00-J22, J32, J34.0, J36, J39.0-J39.1, J44.0, J85, J86, K04.4, K04.6, K04.7, K10.2, K11.3, K12.2, K14.0, K57.0, K57.2, K57.4, K57.8, K61, K63.0, K65.0, K65.1, K65.2, K65.9, L00-L08, L30.3, M00-M01, M46.2-M46.5, M60.0, M65.0, M71.0, M71.1, M72.6, M86, N13.6, N15.1, N15.9, N30.0, N30.8, N34.0, N41.2, N43.1, N45.2, N45.3, N45.4, N48.2, N61, N70, N73, N75.1	This algorithm has not been specifically validated in ARTIS, but the register itself is subject to strict quality assurance routines and has been validated several times.  References:  Ludvigsson et al. External Review and Validation of the Swedish National Inpatient Register, BMC Public Health, 2011 (11):450.  http://www.socialstyrelsen.se/register/halsodataregister/patientregistret/inenglish

090177e1953e1418\Approved\Approved On: 16-Oct-2020 13:21 (GMT)

Event	Operationalisation	Validation ICD

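### The objective promises a rate for all infections, but the only infection endpoint is hospitalised infection, and its code list has gaps that make a rate labelled as overall an undercount

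*Protocol*

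**What the plan says.** The objective in section 8 is "To estimate incidence rates of infections, including serious infections, malignancies, cardiovascular events, and use during pregnancy among RA patients". The front-page information table and the abstract (section 4) word the infection part in the same way. It follows the RMP item listed in section 7, "infections including serious infections (Important Identified Risk" being the label there. This is the only identified risk on that list: malignancy and cardiovascular disease are potential risks, and pregnancy is missing information. Table 2 in section 9.5 has one row for serious infection and another that begins "Any infection (including serious infection".

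The operative sections are narrower. The title names serious infection only. Section 9.3 lists "safety events of special interest including serious infections, all malignancies, CVD events, and use during pregnancy". Section 9.3.3 has one infection endpoint, "Hospitalised infections overall". Annex 1 Table 3 has one infection algorithm, under serious infections: "Hospitalisations in the Patient Register listing as main diagnosis ICD10-codes below. If main diagnosis is RA, contributory diagnoses are also considered". Its genitourinary codes include "N13.6, N15.1, N15.9, N30.0, N30.8, N34.0, N41.2, N43.1", and the list ends at N75.1.

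Section 9.4.3 says that the Patient Register also holds "all visits to non-primary outpatient care". Table 3 does not use those visits for infections.

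**The concern.** There are two separate defects.

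The first is scope. A reader of the objective expects a rate for infections of any severity, with serious infections as a subset. No endpoint or algorithm in the protocol can produce the wider rate. If the report presents the hospitalised rate under the objective as worded, it can be mistaken for an all-infection rate.

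The second is content. An endpoint described as hospitalised infections overall should count an admission for any infection. The fixed code list leaves out some infections that can be the main reason for admission, so the reported rate would be lower than its label implies. This affects the one RMP item classed as an identified risk, in a study whose whole output is incidence rates.

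**Working it through.** **1. Reproduce Table 2.** The inputs are the counts in section 9.5. The exact (Clopper-Pearson) 95% limits for x events in n patients are the 0.025 quantile of Beta(x, n − x + 1) and the 0.975 quantile of Beta(x + 1, n − x).

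| Row | x/n | Proportion | Computed 95% CI | Printed 95% CI |
|---|---|---|---|---|
| Any infection | 22/73 | 0.301 | 0.199 to 0.420 | 0.199 to 0.420 |
| Serious infection | 3/73 | 0.041 | 0.009 to 0.115 | 0.009 to 0.115 |

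The other three rows also reproduce to three decimals. The table is arithmetically correct. The problem is that its first row has no matching endpoint.

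**2. Distance between the two scopes.** From the same counts:

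- serious share of all infections: 3/22 = 13.6% (exact 95% CI 2.9% to 34.9%);
- remainder: 22 − 3 = 19, and 19/22 = 86.4%;
- ratio of the two proportions: 22/3 = 7.3.

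The counts are small. Table 2 does not say that serious in the RMP means hospitalised, so treating the two as equal is an assumption.

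**3. Check of the code list.** The Table 3 list was compared with selected ICD-10 codes. The protocol does not define the codes; their meanings here are those of the standard classification.

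| Code | Standard meaning | In Table 3? |
|---|---|---|
| N10, N12 | Pyelonephritis | No |
| N39.0 | Urinary tract infection | No |
| I33 | Endocarditis | No (the only I codes are I30.1 and I40.0) |
| U07.1, U07.2 | COVID-19 | No (no U code at all) |
| N13.6, N15.1, N30.0 | Other urinary infections | Yes |
| A41.9 | Sepsis | Yes, within A00-B99 |
| J12.8, J18.9 | Pneumonia | Yes, within J00-J22 |

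The N and I gaps fall in the middle of the list, so a table cut short in extraction does not explain them. A U code would come after the last printed code, N75.1, so that absence is slightly less certain.

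**4. Can another code rescue the admission?** Contributory diagnoses count only when the main diagnosis is RA. An admission with N39.0 or U07.1 as main diagnosis and, say, J12.8 as contributory is therefore not counted. One with A41.9 or J12.8 as main diagnosis is counted.

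**5. Calendar time.** The protocol is dated 14 October 2020, Ruxience was approved in the EU on 01 April 2020, and section 6 plans the analytic dataset for 31 December 2023. The protocol does not mention COVID-19.

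**6. Direction and size.** If a share f of infection admissions has an omitted main code, the reported rate is (1 − f) times the full rate. Because f cannot be negative, the error can only be downward. The protocol gives no value for f. As arithmetic only, f = 5% gives a factor of 0.95 and f = 30% gives 0.70; neither is an estimate.

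**The case against.** Much of the protocol is already consistent. The title, the Variables text in the abstract and section 9.3, section 9.7 and Table 3 all speak of serious infections. What conflicts is the objective sentence, which follows the RMP label, and one row of a table that only illustrates precision. This stands, and it makes the first defect one of wording.

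Section 9.7 also gives a reason for the algorithms: they allow the results to be set beside earlier ARTIS findings. If those studies used the same list, replacing it would weaken the comparison. This stands as a reason to keep the list. It is no reason to report only that list under a label that says overall.

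Code-level detail could sit in the statistical analysis plan, which was not available for this review. But the protocol itself fixes the endpoint and prints the list, and section 9.7 says that major changes to primary endpoint definitions would be reflected in a protocol amendment.

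Four stronger readings are tempting, and the protocol does not support them:

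- A reader might infer that the RMP identified risk goes unanswered. Its serious component is estimated; only the non-serious component is not.
- A reader might infer that the study misses 86% of the infections it sets out to count. The hospitalised endpoint is not built to count non-serious infections, and the figure rests on 22 events.
- A reader might infer that the serious-infection rate is low by a known amount, such as 10% to 30%, or that the result will be falsely reassuring. No figure in the protocol supports such a range. Large groups are covered (A00-B99 except A33 and A50, J00-J22, L00-L08, several urinary codes), and in a comparison with earlier results from the same list, stable omissions would affect both sides.
- A reader might infer that an outpatient or dispensing-based infection endpoint is required. Section 9.4.3 describes the Prescribed Drug Register as an aid to classifying DMARD history. Such an endpoint would need its own algorithm and would still lack primary-care diagnoses, so it is a debatable addition.

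**Conclusion.** The point holds in two limited parts.

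First, the objective and the any-infection row of Table 2 are wider than the endpoint. The study as defined estimates hospitalised (serious) infection only. In the RMP counts the any-infection proportion is about 7.3 times the serious one, so the wording matters to anyone reading the rate, although no planned estimate is wrong because of it.

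Second, the Table 3 list does not deliver hospitalised infections overall. Under standard ICD-10 meanings, admissions with pyelonephritis, unspecified urinary tract infection, endocarditis or COVID-19 as the main code fall outside it, and the contributory-code rule does not generally bring them back. The result is an undercount of unknown size. No sample size or power figure is affected. Both parts should be corrected before the interim report planned for 01 July 2023.

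**What to change.** 1. **Wording.** In the front-page table, the abstract and section 8, narrow the infection objective to hospitalised (serious) infections, in line with the title. Either drop the any-infection row of Table 2 or label it as not estimated in this study.
2. **Code list.** Keep the current Table 3 list for comparison with earlier ARTIS results. Beside it, report the hospitalised-infection rate with N10, N12, N39.0, I33 and U07.1/U07.2 added, and show COVID-19 separately. The difference between the two rates then measures the undercount that the protocol cannot quantify.

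The cost is a protocol amendment to the objective text and one table, plus a longer code list applied to data already linked. No new register is needed. The downside is two versions of the infection rate in the report, which must be clearly labelled.

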## 9. RESEARCH METHODS

### 9.1. Study Design

This active surveillance study uses data from the established ARTIS register, an ongoing, prospective, disease-based cohort started in 1999 with the primary aim of evaluating the safety of RA patients who are started on new biologic therapies for RA during routine post-marketed clinical use. This study is a secondary data collection study of anonymised, structured data in ARTIS.

### 9.2. Setting

Sweden is a Scandinavian country with almost 10 million inhabitants. The prevalence of RA in Sweden is around 0.7% and the overall incidence is 41/100,000 per year.

Swedish health-care is tax-funded and offers universal access. Hospital referral is based on geography rather than insurance-status. Patients with RA are typically treated by rheumatologists, the vast majority of whom work in public and hospital-based clinics.

Health and demographic information are collected in a series of registers with a high degree of completeness resulting from the mandatory and semi-automated registration of their data. Based on each Swedish resident’s unique personal identification number, issued to all Swedish residents alive in 1947 or born/immigrated thereafter, linkage of data from different registers is possible. The registers are maintained by governmental bodies (the main registers used in this project are held by the National Board of Health and Welfare (Socialstyrelsen) and Statistics Sweden (Statistiska centralbyrån), who may perform data linkages and provide de-identified data for research purposes.

Use of a RA treatment for a particular patient in Sweden has never been subject to a formal approval process (with the exception of a period during 2002-2003, when manufacturing issues led to reduced availability of etanercept), mandatory treatment history, or disease activity indices. Instead, the Swedish Society for Rheumatology has issued guidelines for the use of biologics, which are revised on an annual basis, but the ultimate decision to treat with biologics and which biologic to use have always resided with the treating rheumatologist.

### 9.2.1. Inclusion Criteria

Patients must meet all of the following inclusion criteria to be eligible for inclusion in the study:

1. Initiation of Ruxience as captured in ARTIS/SRQ.
2. Diagnosis of RA by a consulting rheumatologist.\*
3. Age >18 years at the time of cohort entry.

### 9.2.2. Exclusion Criteria

There are no exclusion criteria for this study.

### 9.2.3. The SRQ and ARTIS

The Swedish Rheumatology Quality Register (SRQ) was started in 1995 by the Swedish Society of Rheumatology to improve the healthcare and treatment for patients with RA. SRQ followed on regional register initiatives, to enable a national real-world documentation of many different aspects of RA and developed over time into a harmonised national register. SRQ was started mainly for patients with RA, but over time it has been expanded to cover several other rheumatic diseases. Initially focusing on early RA, SRQ has gradually come to include other segments. Data entry into SRQ is provided by the patient and the rheumatologist in conjunction with visits. Visits are scheduled according to treatment guidelines and clinical practice, at 0 and 3 to 6 months after the initiation of a new anti-rheumatic therapy, and thereafter in relation to the level of disease activity, according to an overall treat to target paradigm. Data are routinely captured as patients must visit their physician annually to renew prescriptions and must refill prescriptions every 3 months.

Mandated by the Swedish Society of Rheumatology, ARTIS is a research project hosted by the Karolinska Institutet. Since 1999, ARTIS has conducted a safety surveillance programme for immunomodulators based on SRQ linked to additional registers and includes all presently available biologics used for the treatment of patients with inflammatory rheumatic diseases. It covers around 90% of all biologic initiations in Sweden after 1999.

---

[figure not shown]
\* Diagnosis of RA by a consulting rheumatologist is possible for all patients.

To maintain this high amount of data capture, and to improve completeness of data, the Swedish Society for Rheumatology regularly holds scientific meetings during which the surveillance data are presented. The managers and research nurses of ARTIS regularly visit participating centers to support clinicians in managing the web-based forms and/or entering information. In each of the 6 geographical regions, at least one rheumatologist is assigned as responsible for the registration in SRQ. Similarly, the ARTIS steering committee has geographical representation.

By the end of 2018, the follow-up within ARTIS included over 90,000 biologics treatment initiations among approximately 45,000 individuals. The treatment indication was recorded as RA or polyarthritis in 53% of patients [n=23788], psoriatic arthritis (PsA) in 15% of patients [n=6848], ankylosing spondylitis (AS) in 9% of patients [3914], spondyloarthropathies in 8% of patients [n=3540], juvenile arthritis in 5% of patients [n=2159], and the remainder as other rheumatic diseases.

Figure 1 shows the accumulated number of biologic starts across all rheumatology indications in the SRQ. Figure 2 shows the total number of treatment episodes and their distribution across specific drugs.

**Figure 1. Accumulated Number of First Ever Biologics Starts Across All Rheumatology Indications Registered in the Swedish Rheumatology Quality Register and Amenable for Monitoring in the ARTIS Programme**

Dashed line = across all rheumatology indications, bold line= RA. Because of sequential discontinuations and switches to a second or third biologic, the total number of biologics treatment initiations is higher (>80,000 treatment starts).

**Figure 2. Cumulative Number of Treatment Starts in the Swedish Follow-up on Biologics Treatment Across Patients with Rheumatic Diseases**

[figure not shown]

Table 1 below shows the percentage use of biosimilars from 2010 for adalimumab, etanercept, infliximab and rituximab.

**Table 1. Temporal Trends in the Percentage Use of Biosimilars in ARTIS**

Year	Adalimumab	Etanercept	Infliximab	Rituximab
2010	0	0	0	0
2011	0	0	0	0
2012	0	0	0	0
2013	0	0	0	0
2014	0	0.1%	0	0
2015	0	0.4%	57%	0
2016	0	81%	75%	0
2017	0	74%	92%	0
2018	7%	17%	88%	42%

The treating physicians enter the information into the study data-base via a web-based interface. Optionally, it is possible to send the data to the study secretariat on a pre-designed paper form. Patients can enter his/her data through the internet ahead of the visit, at touch-screens in the waiting room, or on paper. The clinical information can be accessed by the treating physician and has been found to be a very useful tool in the management of individual patients. Currently, the vast majority of the rheumatologist-derived data are entered directly via the internet in direct conjunction with the visit, and over half of the patient-derived data are also entered electronically, ahead of the visit.

Safety outcomes included in ARTIS are derived from 2 sources; spontaneous reports of adverse drug reactions (ADRs), and linkage to the national health care registers of Sweden (Section 9.4.2). This study will only utilise the data describing health outcomes derived from national health care registries.

